9.4. Study size

An earlier feasibility assessment estimated that there were 139,061 hospitalized patients with a primary diagnosis of VTE in CDM between 01 January 2017 and 30 August 2022. Among these, 53,918 patients received apixaban and 18,035 received warfarin during the hospitalization. Among the patients receiving apixaban during first VTE hospitalization, 47,029 patients had linked data in Dx and LRx between 01 January 2017 and 30 August 2022. These counts were for informational purposes only and will not represent the actual number of patients to be utilized in the study. Application of other inclusion and exclusion criteria or other factors will reduce the sample size. All eligible participants will be included in the study.

9.5. Data management

Data contributions are subjected to a series of quality checks to ensure a standardized format and to minimize error rates. IQVIA standardizes a limited number of fields, such as gender, place of service and state, for which the standard is easy to define and widely agreed upon. For every active health plan, IQVIA compares the current submission to the previous submission. The frequency distributions of key fields are compared. In addition, basic statistical analyses are generated for key fields to check for trend breaks and data gaps. Data management, calculations and analyses will be performed using SAS, version 9.4 or later (SAS Institute Inc., Cary, NC, USA). Please refer to section 8.7 for details regarding quality control.

9.5.1. Case report forms (CRFs)/Data collection tools (DCTs)/Electronic data record

Not applicable.

9.5.2. Record retention

To enable evaluations and/or inspections/audits from regulatory authorities or Pfizer, IQVIA agrees to keep all study-related records, including study documentation, archived analytic datasets, and adequate documentation of relevant correspondence. The records should be retained by IQVIA according to local regulations or as specified in the study protocol, whichever is longer. IQVIA must ensure that the records continue to be stored securely for so long as they are retained.

If IQVIA becomes unable for any reason to continue to retain study records for the required period, Pfizer should be prospectively notified. The study records must be transferred to a designee acceptable to Pfizer.

Study records must be kept for a minimum of 15 years after completion or discontinuation of the study, unless IQVIA and Pfizer have expressly agreed to a different period of retention via

a separate written agreement. Record must be retained for longer than 15 years or as required by applicable local regulations.

IQVIA must obtain Pfizer's written permission before disposing of any records, even if retention requirements have been met.

9.6. Data analysis

Descriptive statistics will be produced for all relevant study measures previously described, for the overall cohort and for each treatment (apixaban and warfarin). Categorical measures will be presented using frequency (number of patients [n]) and percentage (%) of total study patients observed in each category. Continuous and count variables will be presented as the mean, SD, median, minimum, maximum and IQR. As relevant, continuous variables will also be categorized into intervals. Univariate statistics will be calculated for each measure of interest. No comparisons will be made between the two cohorts..

Four multivariable regression models will be developed for this study. Cox proportional hazards models will be conducted to evaluate both the risk (expressed as hazard ratios with corresponding 95% confidence intervals) of discontinuing or switching from the index treatment as well as the risk of experiencing a clinical event (i.e., recurrent VTE, major bleeding, or CRNM bleeding).. The main effect variable will be the treatment cohort (apixaban vs. warfarin, with warfarin as the reference group). Covariates to be considered for inclusion into the models will include demographic and clinical characteristics of interest. A backward elimination of independent variables least associated with the dependent variable may be used. Clinically relevant covariates that are not retained during backward elimination may also be forced into the model. Collinearity among the variables of interest will be evaluated during model development.

Kaplan-Meier analyses will also be utilized to report the time to an event of interest (e.g., switch, discontinuation). Kaplan-Meier is a method for estimating the probability of the proportion of individuals remaining in the sample at a particular time from an initiation point. It takes into account patients lost or censored before the study endpoint. All analyses will be based on observed, not projected, data. Analyses will be conducted using SAS[®] Release 9.4 (SAS Institute Inc., Cary, NC), and the results will be reported in Excel tables.

Any major modifications of primary endpoint definitions (treatment patterns) or their analyses would be reflected in a protocol amendment.

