9.2.2. Outcome measures

The following outcome measures are assessed post-discharge, and will be measured during the variable post-index period starting on the treatment index date for the apixaban and warfarin cohorts.

Treatment patterns

- Persistent days (mean, SD, median, IQR, min, max) will be reported for patients until they discontinue, switch or end of follow-up based on definitions below
- Patients discontinuing outpatient treatment of apixaban or warfarin, respectively (NDC codes from LRx; n, %)

Note: Discontinuation will be defined as the occurrence of a ≥ 30 day gap from the run-out of days' supply of the treatment (post-discharge) index prescription (i.e. apixaban or warfarin) to the date of the next claim for the respective therapy or with no other claims for the respective therapy. The date of the discontinuation will be defined as the last day of the days' supply of the last filled prescription.

- Time (in days) from treatment index date to discontinuation date (mean, SD, median, IQR, min, max)

Note: Kaplan-Meier (KM) curves will be generated to measure median time (and 95 % CI) to discontinuation.

- Patients switching to an OAC other than apixaban or warfarin, respectively (switched) (NDC codes from LRx; n, %)

Note: Patients will be considered to have switched if they filled a prescription for OAC other than apixaban or warfarin, respectively (identified through NDC codes in LRx) or for PAC within 30 days before or after the run out date of index treatment. The date of the switch will be defined as date of the prescription of such a therapy (OAC or PAC).

- Time (in days) from treatment index date to switch date, defined as the date of the first claim for the new OAC or PAC (mean, SD, median, IQR, min, max)

Note: KM curves will be generated to measure median time (and 95 % CI) to switching

Clinical Outcomes

The following clinical outcomes will be assessed during the time patients are persistent with their respective index apixaban or warfarin treatment (treatment index):

- Patients with ≥ 1 hospitalization for recurrent VTE (ICD-10 codes in CDM; n, %)
- Incidence rate (IR) of recurrent VTE (per 100 patient years)
 - The date of the first observed event will be flagged. The numerator for IR will be the number of patients with the event of interest and denominator will be the ‘at risk’ period i.e. the time to first event. The 95% confidence intervals (CI) will also be reported.

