9.3. Data sources

IQVIA's CDM database will be linked to Dx and LRx for this analysis.

Hospital Charge Data Master (CDM)

IQVIA's Hospital CDM is comprised of hospital-based data which are sourced from hospital CDM files that roll up to the UB-04 files which are submitted for payment. Data covers non-federal, acute-care short-stay hospitals, covering inpatient and outpatient services, including emergency room (ER) utilization with information on diagnoses, procedures, treatment and daily un-adjudicated charge details. Limited patient and hospital characteristics are also available. Data is available from 2001, with a data lag of approximately 6 weeks. The data cover more than 450 hospitals per month and approximately 8 million inpatient visits and 105 million outpatient visits per year. Charge details during a stay are provided on a daily basis (and lack a time stamp). Diagnoses lack a time or day stamp.

It is important to note some limitations of this dataset. Firstly, because this is an open-source database, there is a loss of visibility to healthcare activity and consumption outside of hospitals that participate in/contribute to the database. Secondly, unlike administrative health plan claims data, it is not possible to apply continuous enrollment (CE) requirements. Proxies for CE must be implemented based on hospital reporting to provide greater assurance that patient healthcare activity within this database is captured during the study period. Socioeconomic details, such as race/ethnicity or income, are unavailable in the data. Clinical detail is also limited. Due to patient privacy reasons, a subject who is 85 years or older will only have the recorded age of "85". And finally, only charges are available in CDM, thus a national cost to charge ratio must be applied to charges.

Medical claims (Dx) database

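### The Cox models make no stated allowance for the index hospital, so the apixaban-versus-warfarin intervals may be too narrow, chiefly for discontinuation and switching

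*Combined protocol and SAP*

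**What the plan says.** Section 9.6 (Data analysis) states "Four multivariable regression models will be developed for this study". The Cox models are to estimate "the risk (expressed as hazard ratios with corresponding 95% confidence intervals) of discontinuing or switching from the index treatment" and the risk of recurrent VTE, major bleeding or CRNM bleeding. On the contrast it says "The main effect variable will be the treatment cohort (apixaban vs. warfarin, with warfarin as the reference group". On adjustment it says "Covariates to be considered for inclusion into the models will include demographic and clinical characteristics of interest", with optional backward elimination.

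Section 9.2.2 adds Kaplan-Meier medians with 95% intervals for discontinuation and switching. For the incidence rates it says "The 95% confidence intervals (CI) will also be reported".

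Under Section 9.1.1 a patient qualifies through an inpatient VTE stay recorded in CDM, and the drug given during that stay decides the cohort. Of CDM, Section 9.3 says "The data cover more than 450 hospitals per month". The number of hospitals contributing over the whole selection window is not given.

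Section 9.2.1 collects hospital region, bed count, rural or urban location and teaching status. It lists them under hospitalization characteristics, apart from the demographic and clinical groups from which Section 9.6 draws its covariates.

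Neither Section 9.6 nor the limitations in Section 9.8 mentions clustering by hospital, a robust variance, frailty or stratification.

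**The concern.** The exposure is set inside the hospital, and patients treated in one hospital may share prescribing habits and discharge or follow-up arrangements. The default variance of a Cox model treats patients as independent. When exposure and outcome are both correlated within hospital, that variance understates the uncertainty of the treatment hazard ratio.

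The discontinuation and switching model is the most exposed. Its events are likely to be frequent, and Section 9.6 identifies treatment patterns as the primary endpoints. In a sample of tens of thousands, a small difference between drugs could look firmly established when variation between hospitals is what limits precision.

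**Working it through.** **Inputs from the documents.** Section 9.4: "Among these, 53,918 patients received apixaban and 18,035 received warfarin during the hospitalization", and for apixaban "47,029 patients had linked data in Dx and LRx between 01 January 2017 and 30 August 2022". That feasibility period is 68 months; the selection window in Section 9.1 (January 2018 to November 2022) is 59 months. Section 9.3: more than 450 hospitals per month. I use 450; a larger total would make the clusters smaller. The protocol gives no target sample size, event count, intracluster correlation (ICC) or design effect, so it has no figure to reproduce. Every ICC, spread and event rate below is an assumption.

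**Step 1: cluster size.** 53,918 + 18,035 = 71,953 treated patients (74.9% apixaban), and 71,953/450 = 160 per hospital. Linkage is 47,029/53,918 = 87.2%. Applying it to warfarin as well (assumption) gives 62,760; times 59/68 gives 54,453, or 121 per hospital. If 50% or 20% survive the remaining criteria, 27,227 or 10,891 remain, about 60 or 24 per hospital.

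**Step 2: design effect for the treatment contrast.** With mean cluster size m, DE = 1 + (m − 1) × ICC(treatment) × ICC(outcome). The correct interval is √DE times the default width, and the default interval covers 2Φ(1.96/√DE) − 1. Example: m = 60 and ICCs 0.2 and 0.02 give DE = 1 + 59 × 0.004 = 1.236, width ×1.11, coverage 92.2%.

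| m | ICCs 0 / 0.02 | 0.05 / 0.02 | 0.2 / 0.02 | 0.2 / 0.05 |
|---|---|---|---|---|
| 25 | ×1.00 (95.0%) | ×1.01 (94.7%) | ×1.05 (93.9%) | ×1.11 (92.2%) |
| 60 | ×1.00 (95.0%) | ×1.03 (94.3%) | ×1.11 (92.2%) | ×1.26 (88.0%) |
| 120 | ×1.00 (95.0%) | ×1.06 (93.6%) | ×1.21 (89.3%) | ×1.48 (81.5%) |

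**Step 3: Cox simulation.** One covariate (drug), true hazard ratio 1, about 75% apixaban, 450 hospitals of unequal size, and 400 replicates per row. Hospital effects on the log hazard (SD su) and on the logit of drug choice (SD sx) are normal and independent of each other. Common events occur in about 53% of patients, rare ones in about 3%.

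| Event | m | su | sx | Robust/default SE | Default coverage | Robust coverage |
|---|---|---|---|---|---|---|
| Common | 60 | 0 | 1 | 1.00 | 95.0% | 94.8% |
| Common | 60 | 0.3 | 0 | 1.00 | 96.3% | 96.0% |
| Common | 60 | 0.3 | 0.5 | 1.09 | 92.2% | 95.0% |
| Common | 60 | 0.2 | 1 | 1.14 | 92.7% | 95.8% |
| Common | 25 | 0.3 | 1 | 1.11 | 92.0% | 95.0% |
| Common | 60 | 0.3 | 1 | 1.28 | 86.8% | 95.0% |
| Common | 120 | 0.3 | 1 | 1.52 | 81.5% | 94.0% |
| Common | 120 | 0.5 | 1 | 2.06 | 63.7% | 94.8% |
| Rare | 60 | 0.3 | 1 | 1.01 | 95.5% | 95.3% |
| Rare | 120 | 0.5 | 1 | 1.11 | 91.7% | 94.5% |

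Monte Carlo error is about 1.1 percentage points on coverage.

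With 15,000 patients (15,000/450 = 33 per hospital), about 50% events and su of 0.2 to 0.3, sx of 0.5 to 1.0 gives SE ratios of about 1.0 to 1.2 (default coverage about 91 to 95%). At sx = 1.5 the ratio is about 1.25 to 1.4 (85 to 89%). Robust coverage is roughly 94 to 96% throughout. At su = 0.1 the ratio is 0.99 to 1.10.

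**What the spreads mean.** With a typical hospital at 25% warfarin (logit −1.10), the central 95% of hospitals lie at the inverse logit of −1.10 ± 1.96 × sx. That is 11% to 47% for sx = 0.5, 4% to 70% for sx = 1.0, and 2% to 86% for sx = 1.5.

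**Step 4: single-cohort intervals.** For an incidence rate or Kaplan-Meier median the treatment ICC drops out: approximately DE = 1 + (m − 1) × ICC(outcome). With 45 apixaban patients per hospital (75% of 60), an ICC of 0.01 gives 1 + 44 × 0.01 = 1.44, width ×1.20, coverage about 90%. An ICC of 0.02 gives 1.88, ×1.37, about 85%. An ICC of 0 changes nothing.

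**Step 5: correlated hospital effects.** With correlation 0.3 between the effects on drug choice and on hazard (common event, m = 60, su = 0.3, sx = 1), the mean log hazard ratio is +0.073 when the truth is 0, a hazard ratio of exp(0.073) = 1.08. Robust coverage is then 19%. At 15,000 patients with the same SDs, robust coverage is 86% at correlation 0.1 and 32% at 0.3.

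**The case against.** A reader might infer that the planned intervals are definitely too narrow because hospitals are known to differ in prescribing and aftercare. The documents do not support that. Section 9.6 is silent on the variance estimator and nowhere declares patients independent. No section reports between-hospital variation. The nearest text, in Section 7, says that regimen or setting may affect continuation. It follows a remark on inpatient and observational settings, so it concerns type of setting more than differences among hospitals. If drug choice does not vary by hospital, the treatment contrast loses nothing (Step 2). The largest ratios need wide prescribing spreads or large clusters.

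There is also a case that hospital influence is weakened by design. Section 9.2 admits to the outcome cohort only patients who fill the same drug within 30 days of discharge. What is modelled is later persistence, and Section 9.2.1 allows the index prescriber to be in primary care or cardiology.

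Finally, a sandwich variance does not repair bias. If hospitals favouring one drug also have better or worse persistence, a robust interval sits around the wrong value (Step 5).

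These arguments stand as limits on size and certainty. They do not remove the point: a standard Cox fit following Section 9.6 as written would use the default variance, and if hospital variation is negligible the robust interval will hardly differ. The single-cohort intervals in Step 4 are affected even if prescribing is identical everywhere, provided outcomes vary by hospital. The bias argument calls for a sensitivity analysis in addition to the variance correction.

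**Conclusion.** The point holds conditionally. The plan omits the hospital from the Cox models although patients enter and receive their exposure through it. The default interval for the treatment hazard ratio will be too narrow if both drug choice and outcome vary between hospitals.

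For discontinuation and switching, the SE ratio is roughly 1.0 to 1.2 under moderate assumed spreads at 15,000 patients, and about 1.4 or more with larger clusters or wider spreads. For rare events, taken here as about 3%, it is near 1.0 to 1.1. These figures assume 450 hospitals, normal hospital effects that are uncorrelated with each other, and a single-covariate model; the actual size cannot be fixed from the documents. Specifying a clustered variance is worthwhile because it is inexpensive and affects a primary endpoint.

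**What to change.** Amend Section 9.6 as follows:

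- All Cox models use a robust sandwich variance aggregated by index CDM hospital (in SAS PHREG, COVS(AGGREGATE) with hospital as the ID variable).
- Incidence-rate and Kaplan-Meier median intervals are hospital-clustered where feasible, for example by resampling hospitals.
- The report gives the number of contributing hospitals.
- A sensitivity analysis stratifies the Cox models by hospital, or adjusts for the hospital characteristics already listed in Section 9.2.1, to address hospital-level confounding.

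The Cox variance change is one option in the planned software and needs no new data. The clustered rate and Kaplan-Meier intervals take minor separate programming. Intervals will be slightly wider. Stratification by hospital loses precision, because hospitals whose patients all received one drug contribute nothing to the contrast; it therefore serves better as a sensitivity analysis than as the main model.

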- Demographic characteristics
- Clinical characteristics

Characteristics of hospitalization

- Hospital characteristics

Outcomes

- Apixaban and warfarin treatment rates during hospitalization

- Post-discharge continuity (i.e. persistence of hospitalization treatment/treatment discontinuation or switch)
- Post-discharge treatment patterns among those who continue the same treatment provided during hospitalization (persistent days, discontinuation, switching)
- Post treatment-index recurrent VTE and bleeding hospitalizations

Data sources

IQVIA's CDM database linked with Dx and LRx will be utilized for this analysis. IQVIA's CDM is comprised of hospital-based data which are sourced from hospital CDM files. CDM covers more than 450 hospitals per month and approximately 8 million inpatient visits and 105 million outpatient visits per year. Dx database includes outpatient medical claims which will be necessary for describing baseline clinical characteristics. Dx database captures over one billion pre-adjudicated claims and three billion records obtained annually from approximately 800,000 office-based physicians and specialists. LRx database captures information on dispensed prescriptions sourced from retail, mail, long-term care, and specialty pharmacies. IQVIA has industry-leading coverage in the following channels: 92% coverage of the retail channel, 72% coverage of standard mail service, and 76% of long-term care facilities. LRx will be necessary for describing baseline treatment history and reporting post-index treatment patterns.

Study size

All eligible patients will be included in the study.

Data analysis

Descriptive analysis will be conducted for all relevant study measures for the two cohorts of interest. No comparisons will be conducted in this analysis. Four multivariable regression models or Cox proportional hazards model will be conducted to evaluate factors associated with outcomes of interest. All analyses will be based on observed, not projected data. Analyses will be conducted using Statistical Analysis System® (SAS) Release 9.4 (SAS Institute Inc., Cary, NC), and the results will be reported in Excel tables.

Milestones (tentative)

| | |
|-------------------------|--------------------|
| Protocol approval: | 17 February, 2023 |
| Start of data analysis: | 27 February , 2023 |
| Final results: | 05 May, 2023 |
| Final study report: | 09 June, 2023 |

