7. RATIONALE AND BACKGROUND

Venous thromboembolism (VTE), comprising deep vein thrombosis (DVT) and pulmonary embolism (PE), is a major health concern associated with significant mortality and morbidity. It is the third most common cause of vascular disease-related death and poses a substantial economic burden to the healthcare system. In the United States (US), approximately 1 million people develop symptomatic VTE each year.^{1,2} There are >330,000 hospital admissions for VTE every year in the United States (US).³ Historical data suggests that the rate of hospitalizations for VTE increased from 7.0 to 8.4 per 1,000 discharges in the US.⁴

Management of VTE during an acute hospital encounter involves rapid anticoagulation. Current guidelines recommend continuing anticoagulation therapy post-discharge with vitamin K antagonists such as warfarin, or one of the newer direct oral anticoagulants (DOAC) which do not require PAC bridging therapy.⁵ Over the past decade, the use of DOACs, particularly apixaban to treat VTE has increased dramatically.⁶

There are some gaps in RWE regarding OAC use among patients hospitalized with VTE. First, there is need for RWE regarding the proportion of patients treated with particular OAC during the VTE hospitalization. Second, there needs to be a better understanding of the OAC-related treatment patterns post-discharge following VTE hospitalizations. There is evidence that a large proportion of patients treated in inpatient and observational hospital settings do not fill an anticoagulant prescription post-discharge⁷. Research shows that the choice of treatment regimen and/or setting could influence the likelihood of post-discharge continuation of OAC medication.⁷ This study will investigate the initial treatment patterns during VTE hospitalization and further investigate the treatment patterns and factors associated with poor outcomes among these patients.

The study team, comprised of members from Pfizer and Bristol Myers Squibb (hereon referred to as the 'Alliance'), is collaborating with IQVIA in conducting a study to assess treatment patterns and health outcomes post hospital discharge for VTE.

090177e19cc79c7f\Approved\Approved On: 03-Mar-2023 00:48 (GMT)

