- Comorbidities of interest (ICD-10 diagnosis codes in Dx or CDM; n, %)
 - Acquired immune deficiency syndrome (AIDS)
 - Alcohol/drug abuse
 - Anemia
 - Cerebrovascular disease
 - Coronary heart disease/ischemic heart disease
 - Congestive heart failure
 - Chronic obstructive pulmonary disease (COPD)
 - Coronavirus disease 2019 (COVID-19)

090177e19cc79c7f\Approved\Approved On: 03-Mar-2023 00:48 (GMT)

- Dementia/Alzheimer's disease
- Dyspepsia or stomach discomfort
- Diabetes mellitus
- Hemiplegia/Paraplegia
- Hematologic disorders associated with bleeding (thrombocytopenia)
- Hyperlipidemia
- Hypertension
- Inflammatory bowel disease
- Liver/Gall bladder/Pancreatic disease
- Obesity
- Peptic ulcer
- Peripheral vascular disease
- Pneumonia
- Renal disease
- Rheumatologic disease
- Sleep apnea
- Spinal cord injury
- Thrombocytopenia
- Thrombophilia
- Varicose veins
- Procedures of interest (ICD-10 diagnosis or procedure codes, CPT Codes, HCPCS codes in Dx or CDM; n, %)
 - Orthopedic surgery
 - Central Venous Catheter
- Baseline bleeds (ICD-10 diagnosis or procedure codes, CPT Codes, HCPCS codes in Dx or CDM; n, %)
 - Gastrointestinal
 - Intracranial
 - Others
- History of falls (ICD-10 diagnosis codes in Dx or CDM; n, %)
- Fracture/trauma involving lower extremities (ICD-10 diagnosis codes in Dx or CDM; n, %)

- Medications of interest (NDC or HCPCS codes in LRx or Dx; n, %)
 - Angiotensin-converting enzyme (ACE) inhibitors/Angiotensin receptor blockers (ARB)
 - Antiarrhythmic agents
 - Antiplatelet agents
 - Aromatase inhibitors
 - Beta blockers
 - Erythropoiesis stimulating agents (ESA)
 - Gastroprotective agents
 - Nonsteroidal anti-inflammatory drugs (NSAID)
 - Selective estrogen receptor modulators (SERM)
 - Statins

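### If backward elimination is used in the four Cox models, the ordinary 95% intervals of the weak or null covariates that survive it are not 95% intervals

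*Combined protocol and SAP*

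**What the plan says.** The abstract (section 4, Data analysis) states the purpose of the models: "Four multivariable regression models or Cox proportional hazards model will be conducted to evaluate factors associated with outcomes of interest". Section 7 likewise says the study will "further investigate the treatment patterns and factors associated with poor outcomes among these patients".

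Section 9.6 is the operative text. It says "Four multivariable regression models will be developed for this study" and names one term in advance: "The main effect variable will be the treatment cohort (apixaban vs. warfarin, with warfarin as the reference group"). For the rest it says: "Covariates to be considered for inclusion into the models will include demographic and clinical characteristics of interest". Selection is described in one sentence, "A backward elimination of independent variables least associated with the dependent variable may be used". The next sentence allows clinically relevant covariates that were dropped to be put back, without naming them. Collinearity is to be checked during model development. Results are hazard ratios with 95% confidence intervals.

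The document gives no stay level, no fixed covariate list, no adjustment for selection or multiplicity, no validation step and no exploratory label for covariate results. Section 9.8 cautions that the results show association and not causation.

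**The concern.** A covariate that survives elimination on the same data that supply its interval has been chosen partly because its estimate was far from the null. The usual 95% interval ignores that choice. For a covariate with no real effect, or a very weak one, the printed interval then covers the true hazard ratio less often than 95% of the time.

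The plan offers these covariates as factors associated with discontinuation, switching, recurrent VTE and bleeding. A reader given only a final model could not tell a chance survivor from a real predictor. The plan does not say whether eliminated variables or the size of the search will be reported, and it leaves both the stay level and the forced-in variables to the analyst.

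**Working it through.** The documents give no figure to reproduce, because no stay level or expected number of findings is stated. The stay level is therefore an assumption here, shown over a range.

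**Inputs**
- Candidates, counted from section 9.2.1: 28 comorbidities + 2 procedures + 3 types of baseline bleed + falls + lower-extremity fracture/trauma + 10 drug classes + Charlson index + prescriber specialty = 28 + 2 + 3 + 1 + 1 + 10 + 1 + 1 = 47.
- Age, gender, payer and index year bring this to 51, and the 8 hospitalization characteristics to 59. Thrombocytopenia is listed twice, so 46 is also a fair count.
- Models: 4 (section 9.6). The text names five outcomes and does not say how they map to four models.
- Stay level s: assumed, 0.01 to 0.20.

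**Null factors retained, if every candidate is null:** expected number = 4 × 47 × s.

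**Coverage for a retained null factor:** it is retained when its p-value is below s, and its 95% interval contains 1 only when p exceeds 0.05. Coverage is therefore max(0, (s − 0.05)/s).

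Both formulas were checked by simulating backward elimination with 47 null candidates and a forced treatment term. The simulation used a Gaussian working model as the large-sample analogue of the Cox Wald test, n = 2,000, 400 runs, and pairwise correlation 0 or 0.2.

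| Stay level | Null factors kept, 4 models (formula) | Kept (simulated) | Of these, 95% CI excludes 1 (simulated) | Coverage (formula) | Coverage (simulated) |
|---|---|---|---|---|---|
| 0.01 | 1.9 | not run | not run | 0% | not run |
| 0.05 | 9.4 | 9.6-10.2 | 9.6-10.2 | 0% | 0% |
| 0.10 | 18.8 | 18.9-19.9 | 10.0-10.9 | 50% | 45-47% |
| 0.20 | 37.6 | 38.4-38.6 | 10.0-10.3 | 75% | 73-74% |

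**Sensitivity at s = 0.05**
- Candidate count: 4 × 46 × 0.05 = 9.2; 4 × 51 × 0.05 = 10.2; 4 × 59 × 0.05 = 11.8.
- Share of candidates truly associated: 25% gives 9.4 × 0.75 = 7.1; 50% gives 4.7; 75% gives 2.4.
- A simulation with 20 of 47 truly associated gave 5.5 null factors kept, against 4 × 27 × 0.05 = 5.4.

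**Truly associated factors selected at 0.05.** Let d be the true log hazard ratio divided by its standard error, and Z be normal with mean d and variance 1. Coverage given selection is P(|Z − d| < 1.96 and |Z| > 1.96) / P(|Z| > 1.96). This gives 60% at d = 0.5, 84% at d = 1, and 95-97% from d = 2 to d = 5. The loss is confined to weak effects.

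**Treatment term.** It is named in advance and was never eliminated in the simulation. Its interval covered a true null effect in 92-97% of runs across the settings, with Monte Carlo standard error √(0.95 × 0.05/400) ≈ 1.1 percentage points.

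**Without elimination.** Fitting all 47 covariates in each model would still leave 4 × 47 × 0.05 = 9.4 intervals excluding 1 if every candidate were null. Each interval would then be a genuine 95% interval, reported whatever its result.

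**The case against.** The strongest reply is that this matters little. No objective in section 8 is to identify predictors, section 9.6 makes treatment cohort the main effect, elimination is only permitted, and section 9.8 already urges caution. A global null is implausible for a list that includes prior bleeds, peptic ulcer, thrombocytopenia, antiplatelet agents and NSAIDs when bleeding is an outcome. The collinearity check may also shorten the list.

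Much of this stands. Elimination is optional, so the point is conditional on its use. The figure of nine is close to a ceiling at a 0.05 stay level, and real associations lower it. A reader might infer that the study will report about nine false predictors whose intervals have no coverage. The documents do not support that: they state no stay level, they allow dropped covariates to be forced back in whatever their p-value, and zero coverage applies only to null factors kept at 0.05 or below. Nor does elimination create the nine. That number measures multiplicity and would be about the same in full models.

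The reply does not remove the point. The abstract gives the models the task to "evaluate factors associated with outcomes of interest", so the covariate estimates are meant to be read. The caution in section 9.8 concerns causation, not chance findings from a search. The amendment commitment in section 9.6 covers the treatment-pattern endpoints and their analyses, so it does not reach the recurrence and bleeding models. Leaving elimination optional adds an unrecorded analyst choice.

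**Conclusion.** The concern holds in a conditional form. If backward elimination is used as section 9.6 permits, the ordinary 95% intervals of retained null or weak covariates are not valid. For null factors, coverage is 0% at a stay level of 0.05 or less, about 45-50% at 0.10 and about 75% at 0.20. For very weak true factors selected at 0.05 it is about 60-84%.

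The count of up to about nine null factors over four models rests on 47 candidates, an assumed stay level of 0.05 and no true associations. It falls to about five if half the candidates are truly associated. The coverage figures are large-sample results, and the number of events per model cannot be known from the documents.

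It would go too far to infer that the apixaban-warfarin interval is invalid for this reason, or that strong predictors are misreported. The calculations show near-nominal coverage for both. Whether elimination drops variables needed to control confounding of the treatment contrast is a separate question, not assessed here. This is a correctable weakness in the covariate results. It does not undermine the descriptive objectives.

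**What to change.** In section 9.6, replace the backward-elimination sentence and the sentence on forcing covariates back in with the following commitments.

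- Each of the four models uses one covariate list, written down before any outcome data are seen.
- Collinear or very rare variables are merged or dropped without reference to the outcome; the duplicate thrombocytopenia entry is an obvious case.
- Where events are too few for the full list, a shorter fixed list or a penalised Cox model is used, not stepwise selection.
- Every coefficient is reported, and covariate hazard ratios are described as exploratory.

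A fixed list restores nominal coverage of each interval. It does not remove multiplicity: some null covariates will still have intervals excluding 1. Full reporting and the exploratory description deal with that, and a false-discovery-rate column is optional.

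The cost is revised wording, a longer results table and somewhat wider intervals, mainly in the bleeding and recurrence models. How much wider cannot be judged yet. Section 9.4 gives 53,918 apixaban and 18,035 warfarin inpatients, but it says these are not the study numbers and will shrink, and it gives no linked count for warfarin.
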